8.6.2. Body Weight

At Screening, body weight will be recorded using a calibrated scale at the investigator site.

Any scale used during the study must report weight in either pounds (lb) or kilograms (kg), and be accurate to the nearest 0.2 lb (or 0.1 kg); ie, the device must be able to distinguish a difference between 150.4 lb (68.4 kg) versus 150.2 lb (68.3 kg). The scale must be placed on a stable, flat surface.

At the Randomization visit, an electronic scale will be provided to the participant for their use (at home) for the remainder of the study. Where possible, the same scale should be used for all body weight measurements from the Randomization visit onward.

Weight measurements should be taken under the following conditions, where feasible:

- After void of urine;
- After removal of shoes, socks, bulky layers of clothing and jackets so that only light clothing remains;

- While remaining still during the measurement.

During each weight measurement from Randomization onward, and using electronic scale provided to the participant, body composition data (including total body water, fat mass and fat-free mass, if possible) will be captured via bioelectrical impedance analysis (BIA), as feasible.

8.7. Genetics

8.7.1. Specified Genetics

Genetics (specified analyses) are not evaluated in this study.

8.7.2. Banked Biospecimens for Genetics

A 2-mL blood sample optimized for DNA isolation Prep D1.5 will be collected as local regulations and IRBs/ECs allow.

Banked Biospecimens may be used for research related to the study intervention(s) and anorexia/cachexia. Genes and other analytes (eg, proteins, RNA, nondrug metabolites) may be studied using the banked samples.

See [Appendix 5](#) for information regarding genetic research. Details on processes for collection and shipment of these samples can be found in the laboratory manual.

8.8. Biomarkers

There are no additional biomarkers planned for this study aside from GDF-15 (described in [Section 8.6](#)).

8.8.1. Specified Gene Expression (RNA) Research

Specified gene expression (RNA) research is not included in this study.

8.8.2. Specified Protein Research

Specified protein research is not included in this study.

8.8.3. Specified Metabolomic Research

Specified metabolomic research is not included in this study.

8.9. Immunogenicity Assessments

Blood samples of approximately 6 mL, to provide a minimum of 2 mL serum, will be collected for determination of ADA and NAb as specified in the [SoA](#). Instructions for the collection and handling of biological samples will be provided in the laboratory manual or by the sponsor. The actual date and time (24-hour clock time) of each sample will be recorded.

Samples collected for determination of ADA and NAb may also be used for additional characterization of the immune response, to evaluate safety or efficacy aspects related to concerns arising during or after the study, and/or evaluation of bioanalytical methods, or for other internal exploratory purposes.

Genetic analyses will not be performed on these serum samples unless consent for this was included in the informed consent. Participant confidentiality will be maintained.

Samples will be analyzed using a validated analytical method in compliance with applicable SOPs. Samples determined to be positive for ADA may be further characterized for NAb.

The immunogenicity samples must be processed and shipped as indicated in the instructions provided to the investigator site to maintain sample integrity. Any deviations from the immunogenicity sample handling procedure (eg, sample collection and processing steps, interim storage, or shipping conditions), including any actions taken, must be documented and reported to the sponsor. On a case-by-case basis, the sponsor may make a determination as to whether sample integrity has been compromised.

Immunogenicity information that may unblind the study will not be reported to investigator sites or blinded personnel until the study has been unblinded.

8.10. Health Economics

Health economics/medical resource utilization and health economics parameters are not evaluated in this study.

9. STATISTICAL CONSIDERATIONS

Detailed methodology for summary and statistical analyses of the data collected in this study is outlined here and further detailed in a SAP, which will be maintained by the sponsor. The SAP may modify what is outlined in the protocol where appropriate; however, any major modifications of the primary endpoint definitions or their analyses will also be reflected in a protocol amendment.

9.1. Estimands and Statistical Hypotheses

9.1.1. Estimands

*Estimand related to the **appetite** primary objective:*

Estimand 1 (similar to “hypothetical”) is intended to provide a population level estimate of the treatment effect on the change from baseline Appetite score for PF-06946860 compared to placebo in all evaluable participants under the scenario of no discontinuation of study intervention and without the potential confounding effects of prohibited medications, regardless of the participants’ compliance with dosing (ie, using the Censored analysis set).

- Population: Patients with advanced cancer, anorexia and elevated circulating GDF-15 levels.

- Variable: Change from baseline for the patient reported 7-day recall Cancer-Related Cachexia Symptom Assessment-Appetite score at Week 4.
- Intercurrent Events:
 - a. Discontinuation of study intervention - Data collected after a participant has discontinued study intervention will be censored and treated as missing data.
 - b. Prohibited medications - Data collected after a participant has received prohibited medications, that would modulate the primary endpoint, will be censored and treated as missing data. The list of concomitant medications will be reviewed prior to database lock to determine which would be classed as “prohibited” for this estimand.
 - c. Inadequate compliance - Data collected after a participant has missed a dose will be censored and treated as missing data.

Missing data due to censoring, study withdrawal or other reasons, are assumed to be missing at random.

- Population level summary: Difference in mean change from baseline for the patient reported 7-day recall Cancer-Related Cachexia Symptom Assessment-Appetite score at Week 4 between PF-06946860 and placebo.

This estimand will similarly be applied to the appetite secondary objective (ie, change from baseline at Weeks 1, 2, 3, 5 and 6).

Alternative estimands for the primary objective may be used in order to examine the robustness of the results and will be detailed in the SAP.

Estimand related to the fatigue secondary objective:

Estimand 2 will be similar to Estimand 1, except for the following:

- Variable: Change from baseline for the patient reported 7-day recall Cancer-Related Cachexia Symptom Assessment-Fatigue score at Weeks 1, 2, 3, 4, 5 and 6.
- Population level summary: Difference in mean change from baseline for the patient reported 7-day recall Cancer-Related Cachexia Symptom Assessment-Fatigue score at Week 4 between PF-06946860 and placebo.

Estimands related to the safety and tolerability secondary objective:

There are no defined estimands for the incidence of treatment emergent adverse events and laboratory abnormalities, and these endpoints will be analyzed using Pfizer data standards as applicable.

Estimands related to tertiary/exploratory objectives:

Tertiary/exploratory endpoints may be analyzed using similar estimands or analyzed in a descriptive manner without reference to an estimand. Other supporting estimands may be used for some of the primary and secondary endpoints as a means to examine the robustness of results, compare to available literature and/or be used for future study planning as needed. Details of these estimands and analyses will be presented in the SAP.

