6.3.2. Breaking the Blind

The IRT will be programmed with blind-breaking instructions. In case of an emergency, the investigator has the sole responsibility for determining if unblinding of a participant's treatment assignment is warranted. Participant safety must always be the first consideration in making such a determination. If the investigator decides that unblinding is warranted, the investigator should make every effort to contact the sponsor prior to unblinding a participant's treatment assignment unless this could delay further management of the participant. If a participant's treatment assignment is unblinded, the sponsor must be notified within 24 hours after breaking the blind. The date and reason that the blind was broken must be recorded in the source documentation and CRF.

Part A of this study is participant- and Investigator-blinded and Sponsor-open. Part B of the study will be open to the participant, Investigator, and Sponsor or Sponsor-designate personnel responsible for study monitoring activities (including all site monitoring activities).

The study-specific IRT reference manual and IP manual will provide the contact information and further details on the use of the IRT system.

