6.5. Concomitant Therapy

The date and time of administration of any background and/or concomitant therapies as well as the name and dosage regimen must be recorded.

Hormonal contraceptives that meet the requirements of this study are allowed to be used in participants who are WOCBP (see [Appendix 4](#)).

Prohibited in the 4 weeks prior to first dose of IP and during Part A

- Initiation of new systemic antineoplastic therapy (eg, chemotherapy, immunotherapy) within the 4 weeks prior to the first dose of investigational product or planning to initiate antineoplastic therapy during the 6-week double-blind portion of the study.
- If a participant has recently completed a course of **antineoplastic therapy**, the last dose of that therapy should be at least 4 weeks prior to Randomization.
- Initiation of new treatment prescribed or self-administered and known to have an impact on **anorexia, weight loss or cachexia**, including but not limited to mirtazapine, olanzapine, cannabinoids, within the 4 weeks prior to the first dose of investigational product or during the 6-week double-blind portion of the study; stable (ie, no significant change to dosage or frequency of administration in prior 4 weeks) therapy is permissible.
- Initiation of new treatment with systemic **glucocorticoids** is prohibited within the 4 weeks prior to the first dose of investigational product or during the 6-week double-blind portion of the study; stable (ie, no significant change to dosage or frequency of administration in prior 4 weeks) steroid therapy eg, dexamethasone as part of pre-medication or daily oral prednisone is permissible.

While use of glucocorticoids for antiemetic prophylaxis as part of standard of care treatment protocols is permitted under conditions described here, every effort should be made not to administer such medications within the 7 days prior to the **Day 1 and Week 4 PRO** assessments (see [Section 8.1.1](#)).

Inhaled or topical steroid use is not restricted.

Prohibited in the 3 weeks prior to first dose of IP and during Part A

- **Radiation therapy other than** localized palliative care (eg, pain management for bone metastases) within the 3 weeks prior to the first dose of investigational product or during the 6-week double-blind portion of the study.

Prohibited in the 2 weeks prior to first dose of IP, and during Part A

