9.5. Interim Analyses

As this is a sponsor-open study, the sponsor may conduct unblinded reviews of the data during the course of the study for the purpose of safety assessment, facilitating PK/PD modeling, and/or supporting clinical development.

A formal interim analysis may be performed to assess efficacy and/or safety. Interim analysis results may be used for internal business decisions regarding future study planning, conducting a sample size re-estimation, adapting the study, or stopping for futility. If a formal interim analysis is conducted, details of the timing, objectives, decision criteria and analyses will be documented in an internal charter or in the final SAP.

Following completion of Part A, the data will be analyzed, and a report written. The results of Part A will not be used to make any changes to the design or conduct of Part B.

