### **2.1.3. Additional Estimand(s)**

Estimands related to tertiary/exploratory objectives:

*Tertiary/exploratory endpoints may be analyzed using similar estimands or analyzed in a descriptive manner without reference to an estimand. Other supporting estimands may be used for some of the primary and secondary endpoints as a means to examine the robustness of results, compare to available literature and/or be used for future study planning as needed.*

Additional estimand related to the change from baseline for the patient reported 7-day recall Appetite score (Part A):

**Estimand 3** (similar to “treatment policy”) may be used, dependant on the amount of censored data (based on a blinded review prior to database lock), to assess the robustness of the treatment effect on the primary endpoint. It is intended to provide a population level estimate of the treatment effect on the change from baseline Appetite score for PF-06946860 compared to placebo in all evaluable participants without regard to discontinuation of study intervention or administration of prohibited medications, regardless of the participants’ compliance with dosing (i.e. using the Complete analysis set).

- Population: Patients with advanced cancer, anorexia and elevated circulating GDF-15 levels.
- Variable: Change from baseline for the patient reported 7-day recall Cancer-Related Cachexia Symptom Assessment–Appetite score at Week 4.
- Intercurrent Events:
  - a) Discontinuation of study intervention – All data collected, regardless of a participant’s discontinuation of study intervention, will be included in the analysis.
  - b) Prohibited medications – All data collected, regardless of a participant’s use of prohibited medications, will be included in the analysis.

- c) Inadequate compliance – All data collected, regardless of a participant's compliance (i.e. missed doses), will be included in the analysis.
- Population level summary: Difference in mean change from baseline for the patient reported 7-day recall Cancer-Related Cachexia Symptom Assessment–Appetite score at Week 4 between PF-06946860 and placebo.

This estimand will similarly be applied to the change from baseline at Weeks 1, 2, 3, 5 and 6.

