#### **6.1.1.2. Sensitivity/Supplementary Analyses**

An additional exploratory analysis (for the primary endpoint only), examining the robustness of results for the primary endpoint, may be performed to estimate the treatment effect related to Estimand 3 (as described in Section 2.1.3). The same summaries and analysis as the main analysis (Section 6.1.1.1) will be performed and reported, but applied to the Complete Analysis Set (as described in Section 4).

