## **7. INTERIM ANALYSES**

### **7.1. Introduction**

*As this is a sponsor-open study, the sponsor may conduct unblinded reviews of the data during the course of the study for the purpose of safety assessment, facilitating PK/PD modeling, and/or supporting clinical development.*

*A formal interim analysis may be performed to assess efficacy and/or safety. Interim analysis results may be used for internal business decisions regarding future study planning or stopping for futility. If a formal interim analysis is conducted, details of the timing, objectives, decision criteria and analyses will be documented in an internal charter or in the final SAP (via an amendment).*

*Following completion of Part A, the data will be analyzed, and a report written. The results of Part A will not be used to make any changes to the design or conduct of Part B.*

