## **7.2. Interim Analyses and Summaries**

N/A

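### Does the pre-lock decision on which medications censor appetite scores need an explicit masking rule because Part A is sponsor-open?

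*Protocol*

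**What the plan says.** Protocol 9.1.1 and SAP 2.1.1 define Estimand 1 in the same words. Data after a prohibited medication that could affect the primary endpoint are censored and assumed missing at random. On what counts as prohibited: "The list of concomitant medications will be reviewed prior to database lock to determine which would be classed as" prohibited for this estimand. Neither section says who does this or what they may see.

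Protocol 6.5 gives the candidates: newly started systemic antineoplastic therapy, new agents acting on anorexia, weight loss or cachexia, new systemic glucocorticoids, radiation other than local palliation, and new megestrol acetate. The appetite and weight class is left open: "including but not limited to mirtazapine, olanzapine, cannabinoids".

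On blinding, Protocol 6.3.2 states: "Part A of this study is participant- and Investigator-blinded and Sponsor-open". Protocol 9.5 and SAP 7.1 add that "the sponsor may conduct unblinded reviews of the data during the course of the study". SAP 7.1 also says "A formal interim analysis may be performed to assess efficacy and/or safety", but SAP 7.2 is marked not applicable, so none is currently planned.

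SAP 2.1.3 introduces Estimand 3, the treatment-policy counterpart, which keeps the censored scores. Its use is "dependant on the amount of censored data (based on a blinded review prior to database lock"). SAP 6.1.1.2 repeats that this analysis "may be performed to estimate the treatment effect related to Estimand 3".

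**The concern.** The primary estimand depends on a classification made after the data have accrued, in a trial where the sponsor may already have seen results by arm. If the people who decide whether a borderline drug censors data know the allocation or the appetite scores, they could, even without intending to, drop scores in the direction that suits one arm. The placebo arm has about 13 participants, so one or two such calls could show in the estimate.

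The other safeguards also look weak at first. The only review called blinded is described for another purpose, namely deciding whether to run Estimand 3. That analysis is optional. SAP 6.5.2 counts participants in the Censored and Complete sets, although censoring removes observations, so both sets could hold the same people while Week 4 scores have been dropped. The quantity at stake is the Week 4 difference and its 90% CI, which Protocol 9.2 says will inform internal decisions.

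**Working it through.** **1. The order of the steps.** SAP 2.1.3 needs the amount of censored data, from a blinded review before lock. Under Estimand 1, data are censored for three reasons: stopping study intervention, a prohibited medication, or a missed dose. The second cannot be counted until medications are classified. The classification must therefore come before that blinded review or form part of it. The natural reading is a single blinded pre-lock process.

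Sponsor-open also need not mean that everyone at the sponsor sees allocation. Protocol 8.5, 8.6.1 and 8.9 withhold potentially unblinding results from investigator sites and, as a separate group, from blinded personnel.

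**2. The room for discretion.** Protocol 6.5 fixes the classes, and Estimand 1 narrows them to medications able to affect the appetite score. What remains is the open tail of one class and the judgement of whether existing therapy changed significantly.

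**3. The plan's own scale.** Inputs from Protocol 9.2: SD 4.2, 20:10 completers, true effect 4, one-sided 5%.

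- Standard error = 4.2 × √(1/10 + 1/20) = 1.627.
- Smallest significant difference = 1.645 × 1.627 = 2.68 (plan: 2.7). This is also the 90% CI half-width under the normal approximation.
- Power = Φ(4/1.627 − 1.645) = Φ(0.814) = 79.2% (plan: about 80%).

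**4. One participant.** Take one of 13 placebo participants, 1 SD above the arm mean at Week 4, with equal correlation ρ between visits (assumed) and k visits before censoring. The fitted Week 4 placebo mean moves by

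(4.2/12) × (1 − βρ), where β = kρ / (1 + (k − 1)ρ).

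- ρ = 0.5, k = 3: β = 0.75, shift = 0.35 × (1 − 0.375) = 0.22.
- ρ = 0.7, k = 3: β = 0.875, shift = 0.35 × (1 − 0.6125) = 0.14.
- ρ = 0.5, k = 1: β = 0.5, shift = 0.35 × 0.75 = 0.26.
- No post-baseline visit left: 0.35.

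**5. Whole classes.** A null simulation used 4,000 trials per setting, 27:13 allocation, six weekly visits, a baseline covariate, unstructured covariance by REML, SD 4.2, and 25% dropout spread evenly over visits. Censoring ran from a random start week onward. Degrees of freedom were Week 4 observations minus 3, in place of Kenward-Roger. Usage rates, correlations, start weeks and dropout timing are assumptions. The range is the largest minus the smallest Week 4 difference over all include-or-censor choices. Each cell gives ρ = 0.5 / ρ = 0.7.

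| Ambiguous classes | Use per class | Mean range | 90th percentile | Lower 90% limit above 0, best choice always taken |
|---|---|---|---|---|
| One | 5% | 0.17 / 0.15 | 0.47 / 0.40 | 5.9% / 5.7% |
| One | 10% | 0.29 / 0.25 | 0.68 / 0.58 | 6.3% / 6.1% |
| Two | 5% | 0.34 / 0.29 | 0.77 / 0.66 | 6.6% / 6.5% |
| Two | 10% | 0.58 / 0.50 | 1.15 / 0.99 | 7.5% / 7.2% |

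With a list fixed in advance the last column is 5.1–5.5% (Monte Carlo SE 0.35–0.42 points across all settings), so part of the one-class rise is within simulation error. The half-width with nothing censored is 2.60 / 2.56. The mean range is therefore 0.15/2.56 = 6% to 0.29/2.60 = 11% of it for one class, and 0.29/2.56 = 11% to 0.58/2.60 = 22% for two. All of these scale with the SD. At an assumed SD of 2.5 (2.5/4.2 = 0.60) the mean ranges become 0.09–0.17 and 0.17–0.35, against a half-width of about 1.5.

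A simpler check gives the same order of size: 10,000 null trials, 20:10, a t-test, one class. Choosing with sight of results gives 6.0% (2 active and 1 placebo users), 6.9% (2 and 3) or 7.6% (4 and 2). Choosing without sight gives 5.1–5.3%.

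**6. What the outputs show.** SAP 6.1.1.1 tabulates appetite by arm and timepoint, SAP 5.2.1 includes the number of observations, and SAP 6 applies this to the Censored set. The Week 4 count by arm is therefore reported. If Estimand 3 is run, SAP 6.1.1.2 repeats the same summaries on the Complete set, and the difference between the two counts is the number censored.

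**The case for a change.** The strongest case for a change is that a sponsor-open design removes the usual presumption of blinding, so masking ought to be stated. The blinded review in SAP 2.1.3 is tied to the Estimand 3 decision, does not mention appetite scores, and is not defined for a trial whose sponsor may look at unblinded data. If Protocol 6.5 settled everything, no pre-lock review would be needed. The Week 4 count on the Censored set mixes censoring with dropout and does not separate the three intercurrent events. A clarifying sentence would cost almost nothing.

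Much of this stands as description. No sentence masks the classification, some discretion remains, and the planned tables give no breakdown by reason. It does not carry the change, however. Making Estimand 3 mandatory would show how far the estimate depends on all censoring together; it would not show whether the classification was masked. A count table by reason would improve reporting but leave the primary result as it is. Fixing the whole list beforehand largely restates Protocol 6.5. It also gives up the reason for a late review, which is that concomitant medications in advanced cancer cannot all be foreseen. The case rests on a reading in which the sponsor blinds the count of censored data but not the step that produces it, and nothing in the documents suggests that.

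**Conclusion.** No change to the plan is needed. Followed as written, with the blinded review of SAP 2.1.3 covering the classification it depends on, the plan gives a sound Week 4 estimate. What is missing is a procedural detail that a competent team would supply in its pre-lock review record: a medication listing without allocation or scores, signed off before lock. A sentence saying so in the SAP would be harmless but optional, and no protocol amendment would be called for.

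The possible effect is small. Average shifts are 6–11% of the CI half-width for one ambiguous class and 11–22% for two. Even if the most favourable choice were always taken, the lower limit would exceed 0 in 5.7–7.5% of null trials, against 5.1–5.5% with a fixed list. Those rates describe a decision rule that SAP 5.1 does not apply. They rest on assumed usage of 5–10% per class, assumed correlations and assumed start weeks; nothing in the documents shows that an ambiguous class will arise. The conclusion would weaken if the classification were in fact made by people holding allocation and scores, or if many more participants than assumed started borderline medications.
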